8.2.3.1. Adverse Events

AEs will be graded by the investigator according to the CTCAE version 4.03 and coded using the MedDRA. The focus of AE summaries will be on Treatment Emergent Adverse Events, those with initial onset or increasing in severity after the first dose of study medication. The number and percentage of subjects who experienced any AE, serious AE (SAE), treatment related AE, and treatment related SAE will be summarized according to worst toxicity grades. The summaries will present AEs both on the entire study period. The Safety Analysis Set will be used.

8.2.3.2. Laboratory Tests Abnormalities

The number and percentage of subjects who experienced laboratory test abnormalities will be summarized according to worst toxicity grade observed for each laboratory test. The analyses will summarize laboratory tests in the entire study. Shift tables may be provided to examine the distribution of laboratory abnormalities. The Safety Analysis Set will be used. For laboratory tests without CTCAE grade definitions, results will be categorized as normal, abnormal high/low or not done. Baseline is defined as the latest non-missing value from the pre-treatment period.

8.2.3.3. Study Conduct and Patient Disposition

An accounting of the study subjects will be tabulated. The subject evaluation groups will be listed. The Full Analysis Set will be used. Subject discontinuation from treatment and study will be tabulated and listed separately with their reason for discontinuation. The Safety Analysis Set will be used.

8.2.3.4. Baseline Characteristics

Baseline characteristics such as demographics, prior line of therapy, medical history, baseline Relapse or Refractory, baseline cytogenetic risk, IMWG Diagnosis Criteria, baseline bone marrow plasma cells, ECOG performance status will be tabulated and listed by dose. The Safety Analysis Set will be used.

8.2.3.4.1. Cytogenetic Risk

Cytogenetic risk will be calculated based on:

- If Karyotype is Blank: then cytogenetic risk is “Missing”.
- If Karyotype is Normal: Then cytogenetic risk is “Standard”
- If Karyotype is abnormal:
 - Look for the following in abnormalities or other:
 - Del 17p
 - T(4;14)
 - T(14;16)
 - Cytogenetic Del 13q
 - Cytogenetic Hypodiploidy
 - If collected, Plasma cell labeling index >3%

If any of these exist, then risk is “high” else “standard”.

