7.6.2. Genetic Analysis

Bone marrow aspirates taken before the start of study treatment will be evaluated at local lab for t(4;14)(p16;q32), t(14;16)(q32;q23), 17p13 deletions, t(11;14)(q13;q32), chromosome 13 deletion, ploidy category, and chromosome 1 abnormalities. If some of these cytogenetic assessments cannot be done, site should provide patient's most recent cytogenetic testing results and enter into eCRF. Samples may be taken up to 7 days before the start of study treatment.

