§ These values are based on the serum freelite assay (The Binding Site Group, Birmingham, UK). The involved free light chain must be ≥ 100 mg/L. Each focal lesion must be 5 mm or more in size.

Relapse is defined as progression of disease after an initial response to previous treatment, more than six months after cessation of treatment.

Refractory is defined as resistance to treatment due to lack of response or progression of disease during treatment or within six months after cessation of treatment.

PF-06863135

C1071001

Final Protocol Amendment 9, 28 March 2023

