8.2.3.6.1. Prior Anti-Cancer Therapy

Number and percentage of participants with any prior regimen will be presented along with median and range of number of prior regimens. The number and percentage of participants in each of the following anticancer therapy categories will be tabulated:

- Participants with at least 1 type of prior anticancer treatment;
- Participants with at least 1 prior anticancer radiotherapy;
- Participants with prior IMiDs and type (e.g., lenalidomide, pomalidomide, or thalidomide, Iberdomide, CC-92480);
- Participants with prior PI and type (e.g., bortezomib, carfilzomib, ixazomib);
- Participants with prior anti-CD38 mAb and type (eg, daratumumab, isatuximab);
- Participants who are Triple-class refractory: refractory to at least 1 PI, and at least 1 IMiD, and at least 1 anti CD38.
- Participants who are Quad-class refractory: refractory to at least 2 PI, AND at least 2 IMiD;
- Participants who are Penta-class refractory: refractory to at least 2 PI, and at least 2 IMiD, and at least 1 anti CD38;
- Participants who received at least 2 PIs, 2 IMiDs and 1 anti-CD38;
- Participants with prior Selinexor;
- Participants with prior Elotuzumab;
- Participants with prior transplant and type (autologous or allogeneic);
- Refractory to last line of therapy;

- Type of prior BCMA-targeted therapy (ADC, CAR-T).

The prior anticancer drugs will be coded in the WHO Drug coding dictionary and will be summarized based on the number and percentage of participants by preferred term. A participant will be counted only once within a given preferred term, even if he or she received the same medication at different times unless specified.

Refractory is defined as having progression occurred after regimen during the regimen or discontinuation of the regimen due to progression.

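### SAP 8.2.3.4.1 can file a recorded high-risk lesion as Standard or Missing, and the SAP definition of refractory matches Protocol Appendix 6 on no reading

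*SAP*

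**What the plan says.** **Cytogenetic risk.** SAP 8.2.3.4.1 sorts patients first on a karyotype field.

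- Blank: "If Karyotype is Blank: then cytogenetic risk is" Missing.
- Normal: "If Karyotype is Normal: Then cytogenetic risk is" Standard.
- Abnormal: only here does the rule say "Look for the following in abnormalities or other", followed by del 17p, t(4;14), t(14;16), del 13q, hypodiploidy and, if collected, a plasma cell labeling index above 3%. Any of these gives High; otherwise the patient is Standard.

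Protocol 7.6.2 has the local laboratory evaluate the pre-treatment marrow for "t(4;14)(p16;q32), t(14;16)(q32;q23), 17p13 deletions, t(11;14)(q13;q32), chromosome 13 deletion, ploidy category, and chromosome 1 abnormalities". It does not mention karyotype. It provides for gaps: "If some of these cytogenetic assessments cannot be done", the site supplies the patient's "most recent cytogenetic testing results and enter into eCRF".

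**Refractory.** SAP 8.2.3.6.1 tabulates triple-, quad- and penta-class refractory patients and those refractory to the last line, using this rule: "Refractory is defined as having progression occurred after regimen during the regimen or discontinuation of the regimen due to progression". Protocol Appendix 6, to which inclusion criterion 1 points, says: "Refractory is defined as resistance to treatment due to lack of response or progression of disease during treatment or within six months after cessation". It classes progression after an initial response, more than six months after stopping, as relapse.

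SAP section 2 undertakes to identify places where it differs substantially from the protocol.

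**The concern.** The cytogenetic rule makes one field a gate for all the others. If lesions are recorded separately from the karyotype, a high-risk lesion can sit in the database and never be consulted. The abnormal branch also treats a lesion that was not looked for as if it had been looked for and not found.

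The refractory sentence cannot be programmed without first deciding what it means. Two programmers could derive different class-refractory counts from the same records.

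At stake is how the treated population is described: the share at high cytogenetic risk and the counts of class-refractory patients. The cohorts have no control arm, so these tables tell a reader what kind of patients produced the reported responses.

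**Working it through.** The plan states no figure to reproduce, so the check traces the rules case by case.

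**Cytogenetic rule.** The third column applies the SAP's own lesion list whatever the karyotype field says, and requires the listed lesions to have been tested before Standard is assigned.

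| Karyotype field and lesion data | SAP result | Result without the gate |
|---|---|---|
| Normal, listed lesion recorded | Standard | High |
| Blank, listed lesion recorded | Missing | High |
| Abnormal, listed lesion recorded | High | High |
| Abnormal, listed lesions not all tested, none found | Standard | Missing |
| Normal or abnormal, listed lesions tested and absent | Standard | Standard |

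Of the three rows with a recorded lesion, two change. The fourth row is a separate defect that does not depend on the gate: the final default assigns Standard without requiring any negative result. The normal-karyotype and untested rows move patients only towards Standard. The blank row loses information but assigns no wrong level.

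The share wrongly reported as Standard through the gate would be

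P(normal karyotype) × P(listed lesion recorded, given normal karyotype).

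The documents give neither factor, nor how often listed lesions go untested. No count follows.

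**Refractory rule.** The SAP sentence can be read in two ways. Reading 1 treats the words about the time after the regimen as a slip, leaving progression during the regimen or stopping because of it. Reading 2 takes them literally, as progression during the regimen or at any time afterwards.

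| Case | Protocol Appendix 6 | SAP, reading 1 | SAP, reading 2 |
|---|---|---|---|
| (a) No response, no progression | Refractory | Not refractory | Not refractory |
| (b) Progression on treatment | Refractory | Refractory | Refractory |
| (c) Progression within six months after stopping | Refractory | Not refractory | Refractory |
| (d) Initial response, then progression more than six months after stopping | Relapse | Not refractory | Refractory |

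Reading 1 departs from the protocol in (a) and (c), reading 2 in (a) and (d). Lack of response is missing on both. The SAP does not mark the difference.

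**Reach.** SAP 6.5 uses no covariates for the MTD, 8.1 calls the summaries non-inferential, and 8.2.2 plans no formal efficacy testing. Neither descriptor enters the derivation of DLT, MTD, ORR or DOR.

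**The case against.** The CRF is not in the documents. The karyotype entry may be an overall normal/abnormal result, with individual lesions entered only when it is abnormal. A normal karyotype with a recorded t(4;14) could then not occur, and that branch would cause no error. This stands, and it is why the point is that the rule *can* misclassify. But the SAP does not say what the field covers, and the protocol has the lesions evaluated by name. The SAP also attaches the word cytogenetic only to del 13q and hypodiploidy, which suggests, without proving, that the other lesions may come from a different test.

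Protocol 7.6.2 has a fallback to the most recent results. That fills some gaps, but the SAP has no rule for lesions that remain untested.

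Appendix 6 defines disease status for eligibility, whereas the SAP sentence concerns refractoriness to individual regimens and drug classes. The sponsor may legitimately use a separate definition. It would still have to be coherent and flagged. Similarly, the protocol does not define cytogenetic risk, so the inconsistency is between the SAP's own high-risk list and the way it is applied.

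A reader might infer three stronger conclusions that the documents do not support:

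- That a known, sizeable share of patients is misfiled. No karyotype or lesion frequencies are given.
- That the whole cytogenetic error understates high risk. Blank karyotypes become Missing, and SAP section 7 drops missing data from tables, so their effect on the high-risk share depends on which patients are blank.
- That the reading of ORR against the 30% benchmark in Protocol 9.3 is invalidated. That benchmark is not tied to cytogenetic risk or class-refractory status.

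**Conclusion.** The point holds as a defect in two derivation rules for descriptive tables.

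The cytogenetic rule can report a recorded high-risk lesion as Standard or Missing. This is conditional on the CRF holding lesion results separately from the karyotype field. The default of untested lesions to Standard under an abnormal karyotype does not need that condition.

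The refractory rule is ambiguous, omits lack of response on either reading, and in addition either drops progression within six months of stopping or counts late relapse. It would be wrong to say flatly that it leaves out the six-month window, because that depends on how the sentence is read.

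The tables affected are the high-risk share and the triple-, quad-, penta-class and last-line refractory counts. The change is worth making before database lock because it alters reported counts at little cost.

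**What to change.** In SAP 8.2.3.4.1:

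- Assign High if any SAP-listed lesion is recorded by any method, whatever the karyotype field shows.
- Assign Standard only when the listed lesions were tested and none was found; otherwise report Missing. The labeling index, used only if collected, need not be a condition for Standard.
- State what the CRF karyotype field covers.

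In SAP 8.2.3.6.1, replace the refractory sentence with the Protocol Appendix 6 definition. Alternatively, write a per-regimen definition that includes lack of response and a stated time window, and flag it as differing from the protocol. SAP 8.2.3.4 should also say which definition its baseline relapse-or-refractory row uses, since it gives none.

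The cost is a few derivation lines. More patients will be reported as Missing for cytogenetic risk. The refractory rule will need response and progression dates for each prior regimen, which can be applied only where they were collected.

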8.2.3.5. Treatment Administration/Compliance

Listings and tables by dose level will be provided. Day 1 of a cycle is the date of first dose within that cycle. Each cycle is a 3-week period for Part 1, or 4-week period for Parts 1.1 1C, 1D, 1E, 2A, 2C, 2D, or 2E except cycle 0 for priming dose. The safety analysis set will be used.

The following will be summarized by subject for each dose level:

- Number of subjects per dose level;
- Median and range of number of cycles started per subject;
- Number (%) of subjects starting a cycle (1, 2, 3...);
- Number (%) of subjects with cycle delays;
- Number (%) of dose interruptions (include both known and unknown dates);
- Number (%) of subjects with dose reductions;
- Number (%) of each reason (AE vs. Other) for cycle delays, dose interruptions and dose reductions;
- Time on treatment (median, range).

The following will be summarized by cycle received for each dose level:

- Total number of cycles started;
- Number of cycles started per subject (median, range);

The following will be summarized for cumulative dose by dose level and cycle: Summary statistics (mean, median, standard deviation and range) of cumulative dose and percent of starting dose (compared to Day 1 dose of each cycle).

Listings by subject (ordered by dose level): start date and stop date of each dosing period within each cycle (including records with 0 mg), administered total daily dose for each period, any missed doses with unknown dates (Y/N), number of missed doses with unknown dates, reason for any dosing changes. Listings by subject and each cycle (ordered by dose level): cycle length, total planned dose, administered total dose, percentage of planned dose, dose delay (yes/no), dose reduction (yes/no), and dose interruption (yes/no).

8.2.3.6. Prior, Concomitant, and Further Therapies

Prior, concomitant, and further therapies (drug and non-drug treatments) will be coded by the World Health Organization (WHO) medical dictionary. Summary tables, listings of prior, concomitant, and further therapies will be provided separately.

It should be recognized that most studies are not designed to reliably demonstrate a causal relationship between the use of a pharmaceutical product and an adverse event or a group of adverse events. Except for select events in unique situations, studies do not employ formal adjudication procedures for the purpose of event classification. As such, safety analysis is generally considered as an exploratory analysis and its purpose is to generate hypotheses for further investigation.

8.2.3.6.1. Prior Anti-Cancer Therapy

Number and percentage of participants with any prior regimen will be presented along with median and range of number of prior regimens. The number and percentage of participants in each of the following anticancer therapy categories will be tabulated:

- Participants with at least 1 type of prior anticancer treatment;
- Participants with at least 1 prior anticancer radiotherapy;
- Participants with prior IMiDs and type (e.g., lenalidomide, pomalidomide, or thalidomide, Iberdomide, CC-92480);
- Participants with prior PI and type (e.g., bortezomib, carfilzomib, ixazomib);
- Participants with prior anti-CD38 mAb and type (eg, daratumumab, isatuximab);
- Participants who are Triple-class refractory: refractory to at least 1 PI, and at least 1 IMiD, and at least 1 anti CD38.
- Participants who are Quad-class refractory: refractory to at least 2 PI, AND at least 2 IMiD;
- Participants who are Penta-class refractory: refractory to at least 2 PI, and at least 2 IMiD, and at least 1 anti CD38;
- Participants who received at least 2 PIs, 2 IMiDs and 1 anti-CD38;
- Participants with prior Selinexor;
- Participants with prior Elotuzumab;
- Participants with prior transplant and type (autologous or allogeneic);
- Refractory to last line of therapy;

- Type of prior BCMA-targeted therapy (ADC, CAR-T).

The prior anticancer drugs will be coded in the WHO Drug coding dictionary and will be summarized based on the number and percentage of participants by preferred term. A participant will be counted only once within a given preferred term, even if he or she received the same medication at different times unless specified.

Refractory is defined as having progression occurred after regimen during the regimen or discontinuation of the regimen due to progression.

8.2.3.7. Electrocardiograms (ECG)

Triplet 12-lead ECGs will be performed per Schedule of Activities. The Day 1 triplicate ECG prior to treatment administration will be used as baseline; if it is missing, values from the ECG taken at screening will be used for baseline.

ECG assessments reported by the site will include PR, HR, QT, QRS, and QTcF. A mean score is calculated and reported for any replicate measurements having the same nominal visit. All summary statistics, analyses and figures will be based on the triplicate averaged data. Any data obtained from ECGs repeated for safety reasons after the nominal time-points will not be averaged along with the preceding triplicates.

ECG summaries will include all ECG assessments from the on-treatment period. RR will be derived from HR. Fridericia's correction (QTcF) will be based on the values collected on the CRF. QTcF will be derived from QT and HR in case QTcF is missing using the following formula:

$$QTcF(msec) = QT(msec) / \sqrt[3]{RR(sec)}$$

All ECG assessments will be listed, and those collected outside the on-treatment period will be flagged in the listing.

QTcF will be summarized by maximum on-treatment values using the following categories:

- <450 msec;
- ≥ 450 msec but ≤ 480 msec;
- >480 msec but ≤ 500 msec;
- >500 msec.

Unscheduled assessments will be utilized in addition to planned assessments. Shift tables will be provided for baseline QTcF value versus worst on-treatment value. Results of ECGS done as additional follow-up for prolonged PK $t_{1/2}$ and unscheduled ECG results will be listed but not summarized. Additionally, maximum increases from baseline (including

scheduled and unscheduled assessments) will be summarized based on the following categories:

- Change >60 msec;
- Change >30 msec but ≤ 60 msec;
- Change ≤ 30 msec.

Data listings will contain the means from a triplicate as well as the parameters from each of the 3 ECGs. Note that using the mean value may result in a participant having a measurement that is not represented by an actual ECG.

8.2.5. PK Analyses

8.2.5.1. Pharmacokinetic Parameters

To assess the pharmacokinetics of PF-06863135, the PK parameters detailed in [Section 6.4](#) will be listed and summarized for subjects in the PK analysis set (as defined in Section 5). Missing values will be handled as detailed in [Section 7.1](#). Each PK parameter, if calculatable by data, will be summarized by dose, cycle, and day and will include the set of summary statistics as specified in the table below:

Parameter	Summary statistics
AUC _τ , C _{min} , C _{max} , CL, V _{ss} , and R _{ac}	N, arithmetic mean, median, cv%, standard deviation, minimum, maximum, geometric mean
t _{1/2}	N, arithmetic mean, median, cv%, standard deviation, minimum, maximum
T _{max}	N, median, minimum, maximum

To assess the relationship between the PK parameters and dose, dose normalized AUC_τ and C_{max} will be plotted against regimen, dose (using a logarithmic scale), and will include individual subject values and the geometric means for each dose. Geometric means will have a different symbol than the individual values. The values will be dose normalized (by $\mu\text{g}/\text{kg}$ or mg dose) by dividing the individual values and raw geometric means by dose. A footnote will be added to the plots to indicate that geometric means are presented on the plot.

8.2.5.2. Pharmacokinetic Concentrations

To assess the PK profile of PF-06863135, PK concentrations will be listed; summarized (n, mean, standard deviation, coefficient of variation, median, minimum, maximum, and geometric mean) by dose, cycle, day and nominal time; and plotted for subjects in the PK analysis set (as defined in [Section 5](#)), where missing and BLQ values will be handled as detailed in [Section 7](#) above.

Presentations for PF-06863135 time-concentration data will include:

- A listing of all concentrations sorted by dose, subject ID, period and nominal time post-dose. The listing of concentrations will include the actual sample collection times, and the time of dosing. Deviations from the nominal time will be given in a separate listing.
- A summary of concentrations by dose and nominal time post-dose, where the set of statistics will include n, mean, median, standard deviation, coefficient of variation (cv), minimum, maximum and the number of concentrations above the lower limit of quantification.
- Median concentrations against nominal time post-dose by dose (based on the summary of concentrations by dose and time post-dose), with all doses presented on the same plot.

Two plots will be generated, so that the concentrations can be presented on linear and logarithmic scales.

For summary statistics and median plots by sampling time, the nominal PK sampling time will be used.

8.2.5.3. PD/Biomarker Endpoints

For baseline continuous endpoint data, descriptive statistics, including the mean, standard deviation, median, minimum, and maximum values, will be provided by treatment arm.

Appropriate statistical methods, e.g., multivariate analysis, logistic regression, longitudinal or repeated measure analysis or Cox-regression analysis, may be used to investigate any possible relationship of biomarker levels with PF-06863135 anti-myeloma efficacy, either as a monotherapy or in combination therapy. Summary statistics will be tabulated by visit and treatment group.

8.2.5.4. Population PK and PK/PD Modeling

Pharmacokinetic and PD data from this study may be analyzed using modeling approaches and may also be pooled with data from other studies to investigate any association/correlation between PF-06863135 exposure and biomarkers (e.g., soluble BCMA) or significant safety endpoints. The results of these analyses, if performed, may be reported separately.

